### **8.13 Treatment of Adverse Events**

Treatment of any adverse event is at the sole discretion of the investigator and according to current good medical practice. Any medication administered for the treatment of an AE should be recorded in the patient's eCRF. Refer to Section 6.6.

## 9. PATIENT COMPLETION AND WITHDRAWAL

### 9.1 Patient Completion

A patient will be considered to have completed the study treatment when he/she has been under treatment till Week 112 (= the end of all the scheduled study visits defined as the concluding visit) following first study treatment administration. The term “study activity” refers to physical visits and does not include follow-up contacts (i.e. phone contacts).

Treatment with investigational treatment (ASCI or placebo) should be conducted and completed according to this protocol unless it has to be ended prematurely because of documented disease recurrence, withdrawal due to an unacceptable toxicity, or withdrawal for other reasons (see Section 9.2).

Once the patient has been withdrawn from investigational treatment or has completed treatment, the reason for cessation of treatment must be documented in the patient’s medical records and eCRF.

### 9.2 Patient Withdrawal

Patients who are withdrawn because of AEs must be clearly distinguished from patients who are withdrawn for other reasons. Investigators will follow patients who are withdrawn as result of an SAE/AE until resolution of the event (see Section 8.8).

Withdrawals will not be replaced.

#### 9.2.1 Patient withdrawal from study product administration

A ‘withdrawal’ from the study product(s) refers to any patient who does not receive the complete treatment, i.e. when no further planned dose is administered from the date of withdrawal. A patient withdrawn from the study product(s) may not necessarily be withdrawn from the study as further study procedures or follow-up may be performed as planned in this study protocol.

The investigator will document in the eCRF whether the decision to discontinue further treatment was made by the patient or the investigator and which of the following possible reasons was responsible for withdrawal:

- (Serious) adverse event (including intercurrent illness, unacceptable toxicity),
- Disease progression/recurrence,
- Protocol violation (specify),
- Other, eg. the occurrence of a second tumor that needs therapy (specify).

In this case, the concluding visit will be performed as described in Section 7.3.2.

If the patient refuses or cannot undergo these study procedures, he/she will be considered as withdrawn from study (Section 9.2.2).

### **9.2.2 Patient withdrawal from the study**

A patient will be considered as being withdrawn from the study when he/she does not undergo any further planned study activity after the date of withdrawal.

A patient may voluntarily discontinue participation in this study at any time. The investigator may also, at his/her discretion and in the best interest of the patient, discontinue the patient from participating in this study at any time. In addition, if the sponsor decides to discontinue the study, no further study procedures (including administration of the study treatment) will occur.

Information relative to the withdrawal will be documented on the Study Conclusion page of the eCRF. The investigator will document whether the decision to withdraw from the study was made by the patients or the investigator and which of the following possible reasons was responsible for withdrawal:

- Death (any cause),
- (Serious) adverse event (including intercurrent illness, unacceptable toxicity),
- Disease progression/recurrence,
- Consent withdrawal, not due to an adverse event,
- Lost to follow-up,
- Other (specify).

### **9.3 Screen and Baseline Failures**

A patient was considered to be a screen/baseline failure if the patient signs the ICF, but withdrew before receiving study treatment.

All patients having given consent to undergo MAGE-A3 expression screening upon resection of their tumor were referenced into a screening section of the eCRF, including patients with a negative MAGE-A3 expression.

## **10. STATISTICAL CONSIDERATIONS**

### **10.1 Sample Size Calculation**

The assumptions for the sample size calculations were the following.

- Primary endpoint on which sample size is based is disease free survival (see Section 3.3)
- Hazard ratio of expected disease free survival of recMAGE-A3 + AS 15 ASCI treated patients relative to placebo treated patients that will be significant at the end of study is 0,75.
- Median Disease-Free Survival in the placebo groups is 24 months
- Recruitment period is 4-5 years
- All patients will be observed for a maximum of 5 years from their first study administration and with a minimum of 6 months after treatment completion.
- Null hypothesis H0: "there are no differences in expected disease free survival between the placebo treated patients and recMAGE-A3 + AS 15 ASCI treated patients.
- Alternative hypothesis H1: "the recMAGE-A3 + AS 15 ASCI treated patients have a different disease free survival compared to the placebo treated patients.
- Anticipated drop out percentage is 15 %
- One-sided alpha for final analysis is 0,05
- Power to detect a  $HR = 0,75$  is 50 %. Power to detect a  $HR = 0,65$  is 80 %.
- Randomization: 2 recMAGE-A3 + AS 15 ASCI patients versus 1 Placebo patient.
- Interim analysis planned when 65% of the total number of events have occurred.
- Calculations were done using East 5.3.

Based on these assumptions and in order to reach 155 events\* (see section 10.2), we needed a total of 273 patients for randomization. A total of 182 patients were to be randomized for treatment with recMAGE-A3 + AS 15 ASCI and 91 patients were to be randomized for treatment with placebo. Total number of evaluable patients (15 % drop out percentage) would be 231.

The power to detect a  $HR = 0,75$  (from 24 to 32 months) was 50%. The study would have 65% power if the true  $HR = 0,7$  (from 24 to 34 months) and 80% power if the true  $HR = 0,65$  (from 24 to 37 months).

Due to the Protocol Amendment 4.0, not all analyses described in this section will be performed and no interim analysis will be done. Please see Section 2.6.2 for the rationale.

\* 147 events without interim analysis

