### 10.3 Statistical Analyses

As of Protocol Amendment 4.0, statistical analyses will not be assessed as planned. All clinical data collected in the study will be analysed descriptively. Please see Section 2.6.2 for the rationale.

Patient characteristics, demographics and baseline measurements will be summarized in order to provide a characterization of the patient population. Descriptive statistics, e.g. mean, standard deviation, median, range, frequency distributions as appropriate will be presented for each randomization group: recMAGE-A3 + AS 15 ASCI versus the Placebo arm.

A yearly safety analysis will be performed until all patients have finished the treatment phase (Visit 14) which is 112 weeks after the last patient was randomized. The incidence and severity of all adverse events will be tabulated per treatment group. Treatment related toxicity > grade 2 will be descriptively described in both arms.

The description of the safety data will be performed, first globally then for each of the study arms. The safety analysis will be performed in all patients who are randomized and who received at least one Study Treatment Administration.

The efficacy analysis will be performed including all patients who are randomized and who received at least one Study Treatment Administration.

Disease free Survival (Section 3.3) will be estimated by means of the Kaplan Meier method and comparison between treatment groups will be done by means of the log-rank test.

A Cox proportional hazards model will be applied to correct for treatment effects and to assess the influence of prognostic and confounding factors such as T category, Neo-adjuvant Chemotherapy vs. Adjuvant Chemotherapy vs. no chemotherapy, N category, gender, centre, multifocality of bladder carcinoma (Y/N), age (continuous), presence of Carcinoma in Situ (CIS) and gene profile population.

The analyses of other outcome measurements will be analyzed in an exploratory way with methods appropriate for the type of the variable. Both the safety data and the efficacy data will be summarized by appropriate descriptive statistics.

For each patient entering, the reason for discontinuation (e.g. patient decision, urologists decision, lack of efficacy, adverse events) should be clarified. The description of the reason for discontinuation will be performed.

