All tests of efficacy hypotheses based on between-treatment comparisons will be performed at the 5% level of significance, and will be two-sided. Statistical tests based on within-treatment comparisons will be performed at the 5% level of significance and will be two-sided. No adjustments will be made to nominal significance levels to account for multiple comparisons made on the same data.

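### Section 10.1 sizes the trial at one-sided 5% but Section 10.3 tests at two-sided 5%, so the stated power and significant HR do not belong to the specified test

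*Combined protocol and SAP*

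**What the plan says.** Section 10.1 opens its list with "The assumptions for the sample size calculations were the following". The list includes "One-sided alpha for final analysis is 0,05" and describes the treatment HR "that will be significant at the end of study is 0,75". It gives power of 50% at HR 0.75, 65% at HR 0.70 and 80% at HR 0.65. The target is 155 events with one interim look at 65% of events, and a footnote gives "147 events without interim analysis". The alternative hypothesis in the same list has no direction: "treated patients have a different disease free survival compared to the placebo treated patients".

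In Section 10.3, DFS is estimated by Kaplan-Meier and "comparison between treatment groups will be done by means of the log-rank test". The section ends with a general rule: "All tests of efficacy hypotheses based on between-treatment comparisons will be performed at the 5% level of significance, and will be two-sided".

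Amendment 4.0 is already built into both sections. Section 10.1 adds that "not all analyses described in this section will be performed and no interim analysis will be done". Section 10.3 begins by saying that the planned analyses are replaced by a descriptive analysis of all clinical data, but the log-rank comparison and the two-sided 5% rule still follow it.

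**The concern.** The DFS log-rank test is a between-treatment efficacy comparison, so the Section 10.3 rule covers it. Section 10.1 attaches a different rule to the final analysis. Its own non-directional alternative fits Section 10.3 better than the one-sided alpha listed beside it. No section says which rule applies to DFS.

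Two misreadings follow. A reader may take the power and the significant HR in Section 10.1 as properties of the test in Section 10.3, and so credit the design with more power than that test has. Also, a two-sided DFS p-value between 0.05 and 0.10 favouring the active arm passes under one section and fails under the other. Section 12.8 requires the first publication to follow the analysis laid down in the protocol, and on this point the protocol lays down two.

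**Working it through.** **Inputs, all from Section 10.1 unless noted.** Events D = 147 without an interim (155 with one look at 65%); allocation 2:1; HR 0.75, 0.70 and 0.65; alpha 0.05 one-sided (Section 10.1) or 0.05 two-sided (Section 10.3).

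**Formulas (Schoenfeld, for a log-rank test).** With allocation 2/3 to 1/3:

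- s = sqrt(D × 2/3 × 1/3) = sqrt(147 × 2/9) = 5.7155
- power = Φ(s × |ln HR| − z)
- critical HR = exp(−z / s)
- events needed = (z_alpha + z_power)² / [(2/9) × (ln HR)²]

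Here z = 1.645 for one-sided 0.05 and z = 1.960 for two-sided 0.05.

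**Step 1: reproduce the plan.** The products s × |ln HR| are 1.644, 2.039 and 2.462. Subtracting 1.645 gives power of 50.0%, 65.3% and 79.3%, against the stated 50%, 65% and 80%. The critical HR is exp(−1.645/5.7155) = 0.750, as stated. The events needed for the stated powers are 147.1, 145.8 and 149.9, close to 147. Section 10.1 was therefore computed one-sided, and the word is not a slip.

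**Step 2: apply the Section 10.3 test to the same 147 events.** Only z changes.

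| | One-sided 0.05 | Two-sided 0.05 |
|---|---|---|
| Power at HR 0.75 | 50.0% | 37.6% |
| Power at HR 0.70 | 65.3% | 53.1% |
| Power at HR 0.65 | 79.3% | 69.2% |
| Critical HR | 0.750 | 0.710 |

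The loss is 12.4, 12.2 and 10.1 percentage points, and the critical HR falls by 0.040.

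**Step 3: the HR called significant.** For an observed HR of 0.75 at 147 events, z = 5.7155 × 0.28768 = 1.644. The p-value is 0.050 one-sided and 0.100 two-sided.

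**Step 4: events that a two-sided 5% test would have needed for the stated power, without an interim.** 208.9 (50% at HR 0.75), 194.6 (65% at HR 0.70) and 190.3 (80% at HR 0.65). Rounded up these are 209, 195 and 191, against 147.

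**Step 5: the design with an interim (155 events, look at 65%).** Section 10.1 names no stopping boundary, so the spending functions here are assumptions.

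- Lan-DeMets O'Brien-Fleming type, one-sided 0.05: bounds 2.169 and 1.690; power 51.0%, 66.6% and 80.5%; final critical HR 0.750. This also agrees with Section 10.1.
- Same type, 0.025 per side: bounds 2.547 and 1.990; power 38.8%, 54.8% and 71.0%; final critical HR 0.712.
- Pocock type, 0.025 per side: bounds 2.080 and 2.242; power 34.7%, 49.8% and 66.0%.

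**Step 6: could another two-sided method explain the stated figures?** At 147 events, the Freedman formula with 2:1 allocation gives 40.3%, 57.3% and 74.2%. Schoenfeld with 1:1 allocation gives 41.5%, 58.0% and 74.3%. Neither reaches 50%, 65% and 80%.

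**The case against.** The strongest reply is that the conflict no longer decides anything. Amendment 4.0 withdraws the planned inference (Sections 2.6.2, 3.3 and 10.3), cancels the interim and drops the 2.5-year follow-up. When recruitment was put on hold, 83 of 273 patients had been randomized. If the final number is near 83 (an assumption, since patients already in screening could still enter), 147 events cannot occur. Even with 83 events, the critical HR would be exp(−1.645 / sqrt(83 × 2/9)) = 0.68 one-sided or exp(−1.960 / sqrt(83 × 2/9)) = 0.63 two-sided, so neither 0.75 nor 0.71 would apply. This stands, and it is why the point is minor.

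A second reply is that Section 10.1 is written in the past tense as a record of the sizing, while Section 10.3 looks forward and covers all efficacy tests. On that reading Section 10.3 governs. The reading is reasonable, but the one-sided alpha is tied expressly to the final analysis and no sentence gives Section 10.3 precedence. It also does not rescue the power and significant HR in Section 10.1, which the two-sided test does not deliver.

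Third, a gap of 10 to 12 points is specific to 147 events without an interim. With 155 events and the interim, measured against the stated 50%, 65% and 80%, the gap is 11, 10 and 9 points under the O'Brien-Fleming-type assumption and 15, 15 and 14 under Pocock type. The condition should be kept with the figure, but the conclusion is the same in each case.

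Finally, one-sided sizing is a legitimate choice for a phase II trial. The defect lies in pairing it, without comment, with a two-sided 5% analysis rule.

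**Conclusion.** The inconsistency is real and stands in the current text. Section 10.1 is arithmetically right for a one-sided 0.05 test, but its power and its significant HR of 0.75 are not properties of the two-sided 5% test in Section 10.3. At 147 events without an interim, power is overstated by about 10 to 12 percentage points and the critical HR by about 0.04. These sizes rest on the Schoenfeld approximation, which reproduces the plan's own figures within a point. The figures for the interim design rest on an assumed boundary.

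Severity is minor, because no confirmatory decision now depends on it. What remains is how a DFS log-rank p-value in the band from 0.05 to 0.10 is to be described, and how readers will cite the design's power.

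**What to change.** Leave the one-sided figures in Section 10.1 as the historical sizing basis and add one sentence beside them: *With the two-sided 5% test of Section 10.3, 147 events without an interim give about 38%, 53% and 69% power at HR 0.75, 0.70 and 0.65, and a critical HR of about 0.71.*

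Add one sentence to Section 10.3: *After Amendment 4.0, any DFS log-rank p-value is two-sided, nominal and descriptive.* If only one sentence can be added, this is the more useful one, because it removes the ambiguity about a reported p-value.

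The cost is two sentences. Patients, data, procedures and the historical sample size are unaffected. The only downside is that the lower two-sided power becomes visible.

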## 10.2 Study Populations to be evaluated

### **Total Treated population:**

The Total Treated population will include all treated patients, i.e. all patients with at least one documented dose of study treatment (ASCI or placebo).

The total treated population will be used for the primary analysis of efficacy.

### **According To Protocol (ATP) population for analysis of immunogenicity**

The ATP population for analysis of immunogenicity will include all evaluable patients (i.e. those meeting all eligibility criteria, complying with the procedures and intervals defined in the protocol, with no elimination criteria during the study) who have received at least the 4 first study treatment doses and for whom data concerning immunogenicity post-dose 4 are available.

### **According To Protocol (ATP) population for analysis of efficacy**

The ATP population for analysis of efficacy will include all evaluable patients (i.e. those meeting all eligibility criteria, complying with the procedures defined in the protocol, with no elimination criteria during the study) who have received documented administration of at least the 4 first doses of study treatment and for whom data concerning efficacy endpoint measures are available.

### **Elimination criteria for analysis**

As defined in Section 6.6.2, certain medications are prohibited during study. Among these medications, the following will not require withdrawal of the patient from the study but may determine a patient evaluability in the according-to-protocol (ATP) analysis.

- Administration of immunosuppressants or other immune-modifying drugs during the study period. The use of prednisone, or equivalent, < 0,125 mg/kg/day (absolute maximum 10 mg/day), or inhaled corticosteroids or topical steroids is permitted.
- Administration of a vaccine not foreseen by the study protocol during the period within the prohibited time as specified in Section 6.6.3.
- Administration of immunoglobulins and/or any blood products during the study period.
- Occurrence of a major protocol violation as indicated in Section 7.1.

### 10.3 Statistical Analyses

As of Protocol Amendment 4.0, statistical analyses will not be assessed as planned. All clinical data collected in the study will be analysed descriptively. Please see Section 2.6.2 for the rationale.

Patient characteristics, demographics and baseline measurements will be summarized in order to provide a characterization of the patient population. Descriptive statistics, e.g. mean, standard deviation, median, range, frequency distributions as appropriate will be presented for each randomization group: recMAGE-A3 + AS 15 ASCI versus the Placebo arm.

A yearly safety analysis will be performed until all patients have finished the treatment phase (Visit 14) which is 112 weeks after the last patient was randomized. The incidence and severity of all adverse events will be tabulated per treatment group. Treatment related toxicity > grade 2 will be descriptively described in both arms.

The description of the safety data will be performed, first globally then for each of the study arms. The safety analysis will be performed in all patients who are randomized and who received at least one Study Treatment Administration.

The efficacy analysis will be performed including all patients who are randomized and who received at least one Study Treatment Administration.

Disease free Survival (Section 3.3) will be estimated by means of the Kaplan Meier method and comparison between treatment groups will be done by means of the log-rank test.

A Cox proportional hazards model will be applied to correct for treatment effects and to assess the influence of prognostic and confounding factors such as T category, Neo-adjuvant Chemotherapy vs. Adjuvant Chemotherapy vs. no chemotherapy, N category, gender, centre, multifocality of bladder carcinoma (Y/N), age (continuous), presence of Carcinoma in Situ (CIS) and gene profile population.

The analyses of other outcome measurements will be analyzed in an exploratory way with methods appropriate for the type of the variable. Both the safety data and the efficacy data will be summarized by appropriate descriptive statistics.

For each patient entering, the reason for discontinuation (e.g. patient decision, urologists decision, lack of efficacy, adverse events) should be clarified. The description of the reason for discontinuation will be performed.

All tests of efficacy hypotheses based on between-treatment comparisons will be performed at the 5% level of significance, and will be two-sided. Statistical tests based on within-treatment comparisons will be performed at the 5% level of significance and will be two-sided. No adjustments will be made to nominal significance levels to account for multiple comparisons made on the same data.

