### **2.6.2 Rationale Protocol Amendment 4.0**

GlaxoSmithKline Biologicals recently reported the negative outcome of the MAGE3-AS15-NSC-003 (ADJ) (109493 - EudraCT number: 2007-001283-73) MAGRIT study (A double-blind, randomized, placebo-controlled Phase III study to assess the efficacy of the recMAGE-A3 + AS15 Antigen-Specific Cancer Immunotherapeutic as adjuvant therapy in patients with resected MAGE-A3-positive Non-Small Cell Lung Cancer (53). The analysis of MAGRIT confirmed the absence of treatment effect in any of the primary, secondary, or exploratory analyses. All aspects of the MAGRIT study have been carefully assessed, and unfortunately these investigations failed to identify a root cause for the lack of efficacy of the MAGE-A3 Antigen-Specific Cancer Immunotherapeutic (ASCI) in NSCLC that could be corrected in ongoing studies, including the MAGNOLIA study.

Furthermore, a comprehensive review of the Phase III results, together with all other available clinical and laboratory data with various recombinant proteins tested in different diseases and settings now suggests that the anticancer activity of this technology may well be limited to a

subgroup of Stage III melanoma patients with a specific predictive gene signature (52). A few patients in early metastatic melanoma also appear to benefit from this type of treatment.

Consequently, GSK Biologicals has decided to stop further development of recMAGE-A3 + AS15 as a standalone treatment for cancer patients. This decision is not motivated by any safety concern as confirmed by all Independent Data Monitoring Committees (IDMCs) overlooking the ASCI trials.

This decision implies that MAGE-A3 +AS15 CI will not be available for future treatment of bladder cancer patients which warrants a substantial amendment (4.0) of the MAGNOLIA study.

As of 23 September 2014, the recruitment was put on hold (sites were still allowed until 3 February 2015 to randomize patients that signed the informed consent or were in the screening process). As of Protocol Amendment 4.0, the recruitment will be stopped and the study population will be unblinded.

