For patients randomized to the placebo group, no further protocol visits will be performed except for the concluding visit and no further doses will be administered. As it cannot be excluded that one or more patients may benefit from this treatment on an individual basis, patients receiving active treatment (patients not on placebo, and patients that have not already completed or interrupted their MAGE-A3 ASCI treatment) will be offered the option to continue the administration of the study treatment until the last dose is administered or until recurrence, whichever comes first, or until the patient or the investigator decides to stop the study treatment. Therefore, the study will continue only with patients from the active treatment group who will decide to stay in the study. Treatment will not be possible anymore after 30 November 2016.

During the treatment period, safety monitoring will continue as initially foreseen during the treatment period. In the best interest of the patient, additional biological samples for protocol research purposes (evaluation of the immune response, translational research) will not be taken nor collected.

The primary and secondary objectives will not be assessed as planned. All clinical data collected in the study will be analysed descriptively. By default, for each biological sample already collected in the scope of this study and not tested yet, testing will only be done if a scientific rationale remains relevant despite the premature termination of the study. In that case, testing will be in compliance with the protocol and ICF signed by the patient. The immune response will not be evaluated anymore as the immune response to IP administration was confirmed in other ASCI trials, but did not show any correlation with the potential efficacy.

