As of Protocol Amendment 4.0 primary and secondary objectives of the MAGNOLIA study will not be assessed as planned. All clinical and safety data collected in the study will be analysed descriptively. Additional biological samples for protocol research purposes (evaluation of the immune response, translational research) will not be taken nor collected. By default, for each biological sample already collected in the scope of this study and not tested yet, testing will only be done if a scientific rationale remains relevant despite the premature termination of the study. In that case, testing will be done in compliance with the protocol and ICF signed by the patient. The immune response will not be evaluated anymore as the immune response to IP administration was confirmed in other ASCI trials, but did not show any correlation with the potential efficacy. See for rationale Section 2.6.2.

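### After Amendment 4.0 only active-arm patients who opt in keep adding safety data, but Section 10.3 gives its per-arm adverse event tables no cut-off at unblinding

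*Combined protocol and SAP*

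**What the plan says.** Section 2.6.2 (Rationale Protocol Amendment 4.0) states that "the recruitment will be stopped and the study population will be unblinded". For placebo patients, "no further protocol visits will be performed except for the concluding visit and no further doses will be administered". Active-arm patients who have not completed or interrupted treatment may continue if they wish. Their safety monitoring carries on as before, and doses are possible until 30 November 2016.

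Recording windows follow treatment. Under Section 8.6, non-serious adverse events (AEs) are recorded from the first dose to 30 days after the last one, and serious adverse events (SAEs) to the concluding visit. Section 8.3 also ends the recording of potential immune-mediated diseases (pIMDs) at the concluding visit.

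Section 3.2 gives the amended analysis plan: "All clinical and safety data collected in the study will be analysed descriptively". Section 10.3 says that analyses will not be carried out as planned and that clinical data will be described. It then keeps this rule: "The incidence and severity of all adverse events will be tabulated per treatment group". It also describes related toxicity above grade 2 in both arms. The population is defined as follows: "The safety analysis will be performed in all patients who are randomized and who received at least one Study Treatment Administration". The safety analysis is repeated yearly until every patient has passed Visit 14, which is later than the unblinding.

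**The concern.** Before the amendment both arms had the same planned observation time. Afterwards, observation time depends on the arm: it stops soon after unblinding for placebo patients and runs on for active patients who opt in. A proportion of patients with an event, taken over all collected data, mixes that difference in follow-up with any difference in risk. The tilt is systematic and goes against the active arm.

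A second problem does not depend on the length of follow-up. Under Section 8.7.2 the investigator judges causality. After unblinding the investigator knows the arm, and nearly all new judgements concern active patients. They would enter the same related-toxicity summary as the blinded ones.

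With the efficacy objectives no longer assessed as planned, the descriptive safety table is one of the main results that the trial will still report.

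**Working it through.** The plan gives no adverse event rate or expected difference, so there is no figure of its own to reproduce. The check asks what the table would show if treatment had no effect on adverse events.

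**Inputs from the documents**
- Recruitment lasted 40 months (Section 4). It was put on hold on 23 September 2014, but "sites were still allowed until 3 February 2015 to randomize patients that signed the informed consent or were in the screening process" (Section 2.6.2).
- The last possible dose is on 30 November 2016 (Section 2.6.2).
- The concluding visit is at week 112 in Table 5 (Section 7.3.2 puts it at about week 120). The calculation uses week 112, which is 112 × 7 / 30.44 = 25.76 months.
- Median disease-free survival is 24 months on placebo (Section 10.1). It is applied to both arms, with recurrence or death ending observation: λ = ln 2 / 24 = 0.0289 per month.
- Dropout is 15% (Section 10.1).
- 83 patients were randomized at the hold (Section 5.1), 2:1, so about 55 and 28.

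**Assumptions:** uniform accrual; unblinding 1, 4 or 8 months after 3 February 2015; opt-in share 40% to 100%; first-event hazard h, equal in both arms. Scenario A has accrual to 3 February 2015, no dropout, and windows closing at unblinding. Scenario B has accrual ending at the hold, 15% dropout by month 25.76, and a one-month tail to the concluding visit.

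**Formulas** for a patient with window c months, no dropout and constant h:
- mean observation = (1 − e^(−λc)) / λ
- probability of an event = h/(h+λ) × (1 − e^(−(h+λ)c))

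The window c is the smaller of 25.76 and the time from entry to unblinding (placebo, and active patients who stop) or to 30 November 2016 (active patients who continue). Results are averaged over entry dates.

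**One patient, by hand.** Take entry 12 months before unblinding, unblinding at 4 months, and h = 0.02, so h/(h+λ) = 0.02/0.0489 = 0.409.
- Placebo, c = 12: 0.409 × (1 − e^(−0.587)) = 18.2%.
- Continuing active, c = 25.76: 0.409 × (1 − e^(−1.259)) = 29.3%.

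Patients who entered early enough to finish, or who recurred or died before unblinding, have the same window in both arms. This dilutes the effect.

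**Averaged over entry, 2% per month, 80% opt-in**

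| Scenario | Unblinding (months) | Months observed, active vs placebo | Incidence, active vs placebo | Excess (points) |
|---|---|---|---|---|
| A | 1 | 17.2 vs 13.5 | 27.8% vs 22.5% | 5.3 |
| A | 4 | 17.4 vs 14.7 | 28.2% vs 24.3% | 3.9 |
| A | 8 | 17.6 vs 15.9 | 28.6% vs 26.2% | 2.4 |
| B | 1 | 16.5 vs 14.5 | 26.8% vs 24.1% | 2.7 |
| B | 4 | 16.6 vs 15.3 | 27.0% vs 25.2% | 1.8 |
| B | 8 | 16.8 vs 16.0 | 27.3% vs 26.3% | 0.9 |

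**Sensitivity**
- 2% per month, 40% to 100% opt-in: excess 0.5 to 6.7 points.
- 5% per month, 80% opt-in: up to 8.5 points.
- 0.5% per month, 40% to 100% opt-in: ratio 1.02 to 1.33.
- Late onset (0.5% per month, only after month 12), 40% to 100% opt-in: ratio 1.06 to 1.75.
- Early reactions (months 0 to 3 only), 80% opt-in: 0 to 0.3 points.

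**Precision.** Near 26% incidence, the standard error of the difference is √(0.26 × 0.74 × (1/55 + 1/28)) = 0.102, about 10 points.

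**Would one remedy do?** Person-time alone would not. For late-onset events the rate ratio on all data is still 1.07 to 1.26 at 80% opt-in, because the extra active-arm time falls where the hazard is higher. A cut-off alone nearly does. With doses 84 days apart, (84 − 30)/84 = 64% of placebo patients in maintenance have a non-serious window that closed before unblinding, by 54²/(2 × 84) = 17 days on average over all of them. The remaining excess is 0.1 to 0.3 points.

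**The case against.** The strongest reply is that this is silence, not a wrong method. Section 10.3 opens by saying that analyses will not be assessed as planned, and it still carries a log-rank test and a Cox model, so the adverse event sentence may also be carried-over text. Section 10.1 says that "not all analyses described in this section will be performed and no interim analysis will be done". Incidence is not defined, and the allowance for appropriate descriptive statistics would permit rates or a split. All of this is fair. A reader might infer that the plan orders post-unblinding events to be pooled into one comparison. No sentence says so; that reading comes from combining the rule to describe all data with the rule to tabulate by group. What remains is that the tabulation is descriptive, fits the amended plan, and is the only rule given for summarising adverse events by arm. Followed as written, it gives a tilted table.

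A second reply is that the effect is small. This stands too. Section 10.3 plans tests for efficacy only, every excess quoted above is below the standard error, and early injection reactions hardly move. In the model only about 16% to 43% of patients are still under observation at unblinding; at 80% opt-in that is roughly 7 to 19 of 55 active patients.

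A third reply is that the 30-day window already handles exposure. It ties recording to exposure but does not equalise it between arms.

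**Conclusion.** The point holds as a minor improvement. The direction is predictable whenever some active patients continue and the denominator is patients treated. The size is not determined by the documents and rests on assumed hazard, opt-in share, unblinding date and accrual shape. At 2% per month it is about 0.5 to 6.7 points. Relative distortion is largest for late-onset events.

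Two stronger readings are tempting and should be resisted. First, the two scenarios are illustrations, not bounds: a higher hazard already exceeds their 2% figures. Second, a simpler calculation that stops every placebo patient at week 24 or 48 and follows continuing active patients to week 112 gives 4.5 to 51 points. It ignores staggered entry, patients already finished, recurrence and the November 2016 stop, so it shows the direction but not a credible size. Nor do the documents support calling this an inflated error rate, since no adverse event test is planned.

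**What to change.** Add to Section 10.3:

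1. Between-arm tables of AEs, SAEs, pIMDs and related toxicity use events up to unblinding, by one date rule stated in advance and applied to both arms.
2. These tables also give events per patient-year, based on each patient's actual recording window. This supplements the cut-off and does not replace it.
3. Safety data after unblinding, including placebo events found up to the concluding visit, are reported separately by arm and labelled open-label. The continuing active-arm follow-up is also labelled uncontrolled.

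A common 30-day window rule for non-serious events in both arms is optional, given the 0.1 to 0.3 points that it removes.

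The cost is a few sentences, a date filter and an exposure denominator in the programs; no new data are needed. The downside is that post-unblinding events leave the between-arm tables, though they are still reported.
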